2.3.2 KNOWN POTENTIAL BENEFITS AND THEIR ASSESSMENT

No claim is made in communications with study subjects (whether providers or patients) that any personal benefit will accrue from participating in this project.

PCPs will have no defined benefits from participating in this project. However, the decision support designed to optimize CKD care may serve to familiarize some providers with new and potentially useful information that can be used to improve the clinical care they deliver in the present or the future. No providers or patients will receive monetary compensation for any aspect of the study unless specifically recruited and consented for interviews to assess the CDS design or experience.

As documented in this proposal, there are major existing deficits in the quality of CKD care delivered in primary care clinics nationally and internationally. Improved CKD care can reasonably be expected to reduce the burden of morbidity or mortality related to progressive renal disease and major cardiovascular events. If the interventions fail to improve CKD care, this knowledge will also be important since it will direct the attention of investigators to other, potentially more fruitful lines of investigation. Thus, regardless of specific findings, the results of this trial will provide important new knowledge that will ultimately contribute to improved care for adults with CKD.

3 OBJECTIVES AND ENDPOINTS

OBJECTIVES Impact of the intervention on:	ENDPOINTS	GUIDELINE JUSTIFICATION FOR ENDPOINTS*
Primary		
1. provider-diagnosed CKD for patients with no documented CKD diagnosis (recognition care gap)	1. Provider-diagnosed CKD in the 18-month period after an index visit	(a) Diagnostic classification of CKD based on eGFR and albuminuria category;
2. ACEI/ARB orders for patients with diagnosed hypertension or nephropathy and no current ACEI/ARB (ACEI/ARB care gap)	2. ACEI/ARB orders in the 18-month period after an index visit	(b) use of ACEIs or ARBs in adults with diabetes and UMACR 30-300 mg/g OR all patients with UMACR >300 mg/g;
3. recommended BP control for patients with consecutive elevated BP (BP care gap)	3. Recommended BP control by the end of the 18-month period after an index visit	(c) BP control to <140/90 mm Hg in adults with CKD and normal UMACR <30 mg/g OR <130/80 mm Hg in adults with ACR >300 mg/g;

OBJECTIVES Impact of the intervention on:	ENDPOINTS	GUIDELINE JUSTIFICATION FOR ENDPOINTS*
4. recommended blood glucose control for patients with elevated A1c (glucose care gap)	4. Recommended blood glucose control by the end of the 18-month period after an index visit	(d) Glycemic control using individualized A1C targets of less than 7% or less than 8% in patients with limited life expectancy, cognitive impairment, or increased risk of hypoglycemia;
5. rates of consultation with nephrology for patients with stage 4 CKD or stage 3b CKD and UMACR >30 mg/g and no recent consultation with a nephrologist (nephrology care gap)	5. Nephrology consultation in the 18-month period after an index visit	(e) Timely nephrology care
Secondary		
a) Use of non-steroidal anti-inflammatory drugs (NSAIDs) b) Medication adherence c) Treatment heterogeneity d) Treatment intensification among patients not at their BP or glucose goals e) CKD treatment patterns across PCPs f) safety issues, including hypotension, hypoglycemia, and electrolyte disturbances, emergency department (ED) visits, hospital admissions for renal and non-renal causes, major CV events, and mortality as deemed necessary per the data safety and monitoring plan g) Understand provider perspective in development of the prototype of the CDS	a) Rates of NSAID use b) Medication adherence scores to blood pressure and glycemia medications c) Treatment heterogeneity d) Rates of treatment intensification among patients not at their BP or glucose goals e) Variations in CKD treatment patterns across PCPs f) safety issues, including hypotension, hypoglycemia, and electrolyte disturbances, emergency department visits, hospital admissions for renal and non-renal causes, major CV events and mortality g) Provider experience with the CKD-CDS tools based on interview data	
Rates of treatment intensification, variations of CKD care across PCPs and overall treatment heterogeneity are indicators of provider utilization of the CKD-CDS.
 
On the patient side, treatment heterogeneity and care disparities are additional measures of overall quality of care.
 
We have a data safety and monitoring plan that includes assessing safety issues like hypotension, hypoglycemia, electrolyte disturbances and ED visits among others.
 
End user experience is important for future scaling up if the intervention is successful

* The endpoints for this study correlate with strongly rated recommendations for slowing progression of CKD in multiple clinical guidelines⁵⁻⁷.

4 STUDY DESIGN

[figure not shown]
4.1 OVERALL DESIGN

- A statement of the hypothesis: CKD is a common and serious chronic disease that often leads to end-stage renal disease and major cardiovascular events. Although evidence-based CKD care can slow

disease progression and avert complications, less than 10% of CKD patients currently receive major elements of CKD care in a timely fashion. We hypothesize that the intervention will 1) Improve identification of adults with CKD at primary care encounters; (2) Increase the appropriate use of renoprotective antihypertensive medications, improve blood pressure control, and improve glycemic management in patients with diabetes through personalized evidence-based treatment options; and (3) Increase collaboration and consultation with nephrologists.

- Phase of the trial: 3
- A description of the type/design of trial to be conducted: This study is a prospective, 2-arm, cluster randomized trial, randomizing primary care clinics at HealthPartners and Park Nicollet to intervention and usual care arms. It is a single site study.

Figure 3: Study Design

- A description of methods to be used to minimize bias: Covariate-based constrained randomization using a computer-generated allocation scheme was used to enhance balance across study arms on key factors. This method enables multiple factors to be balanced between treatment groups and can increase statistical power beyond simple randomization.
- Name of study intervention: Chronic Kidney Disease Clinical Decision Support (CKD-CDS), also known as CKD Wizard
- Name of sub-studies, if any, included in this protocol: None

4.2 SCIENTIFIC RATIONALE FOR STUDY DESIGN

The CKD-CDS intervention provides timely, data driven information to providers at primary care visits with patients who have CKD and a deficit in CKD care. Because it is common for patients to see more than one clinician over time, particularly in the same clinic, there is significant risk of contamination if the intervention were to be randomized at the patient or provider level. However, patients tend to receive most of their care over time at a single clinic, and clinicians tend to practice at a single clinic. For this reason, contamination risk across clinics is relatively low. The cluster-randomized trial design

randomizes primary care clinics to usual care or CKD clinical decision support to minimize risk of contamination.

Clinics were randomly allocated 1:1 to intervention or usual care based on the results of a computer-generated algorithm. From the time the CKD-CDS tool was implemented in April, 2019, through March, 2020, the CKD-CDS interface was programmed to display at eligible visits in clinics randomized to the CKD-CDS intervention group. As a result, intervention-eligible patients were exposed to the intended treatment at visits that took place in a clinic assigned to the same treatment group as their index visit clinic.

The care systems responded to the COVID-19 pandemic in March, 2020, by closing or realigning many of the randomized clinics, making significant changes to the clinics at which providers practiced and shifting from in-person to telehealth visits. The clinic closures and changes in provider locations disrupted what had been reliable correspondence between patients and clinic locations; and hence, made exposure to the intended treatment group unreliable. The shift in visit modality made it very difficult to access the CKD-CDS interface (i.e., the intervention) during visits. Index visits were suspended as of March, 2020, and the CKD-CDS interface was turned off between March and August, 2020, to prevent unreliable intervention delivery and technological challenges.

CKD-CDS delivery resumed in August, 2020 and included all patients who had an index visit at a randomized clinic through March, 2020. The clinic-randomized treatment group that was assigned at each patient's index visit followed each study-eligible patient to all of their post-index visits regardless of clinic location (intervention, control) or modality (in-person, phone, video). This programming change was made to preserve the patient-within-randomized-clinic structure, and maximize treatment fidelity. Programming treatment group assignment to follow the patient enabled the intended treatment to be delivered to patients at post-index visits, even when those visits take place with different providers or at different clinics.

Some provider contamination and learning effects are possible to the extent that intervention patients may have post-index visits with providers from control clinics. Because patients tend to continue seeing their index providers over time, control clinic providers' exposure to the intervention through seeing intervention patients is unlikely to be frequent enough for sustained learning.

The pragmatic study design improves generalizability to real world clinical settings.

4.3 JUSTIFICATION FOR DOSE

Not applicable

4.4 END OF STUDY DEFINITION

The end date for the study is defined as the date that corresponds to 18 months after the index visit of the last person enrolled at a study clinic during the 11 month patient accrual period. Note that the accrual period was shortened from 12 to 11 months due to the onset of the Covid-19 pandemic in March 2020. The pandemic also caused disruptions in care delivery and decreased volume of primary care encounters in mid-2020 which interrupted intervention delivery during this period. We extended the follow-up period from 12 months to 18 months to increase the number of patients with primary care encounters and follow-up measures needed to assess intervention impact.

5 STUDY POPULATION

5.1 INCLUSION CRITERIA

Clinics are the primary unit of randomization. Medical group leaders at HPMG and PN agreed to enroll at least 30 primary care clinics in this study and provided letters of support. In order to be eligible for the study, a clinic was required to meet the following requirements:

- 1) Be a HealthPartners Medical Group or Park Nicollet care system clinic
- 2) Have an established adult primary care department within the clinic (family medicine, adult medicine, and/or combined pediatrics/internal medicine)
- 3) Have a minimum of 20 study eligible patients
- 4) Have access to a nephrologist or nephrology clinic within reasonable geographic proximity

Eligible Adult Patients:

Patients with an encounter with a primary care provider (general internist, family medicine physician, advanced practice nurse or physician assistant) at a study clinic were eligible for the CKD-CDS if the following criteria were met:

- 1) Aged 18 to 75 years, inclusive on their index date. The evidence-based guidelines on which the CDS intervention is based are not applicable outside this age range.⁶²
- 2) Have laboratory evidence of CKD based on eGFR values <60 cc/min/1.73m², including the most recent eGFR value on or prior to index date, and the closest previous eGFR done at least one week prior
- 3) Have one or more CKD care components suboptimally managed at the time of the index visit.

		suboptimally managed if
CKD recognition care gap	1.1) CKD not documented in the electronic health record	1.1) ICD-10 codes N18.3, N18.4, N18.5, N18.6, N18.9 at <2 outpatient encounters, and not on the problem list, in the previous 2 years
ACEI / ARB care gap	2.1) stage 3 CKD; and 2.2a) diagnosed hypertension, or 2.2b) nephropathy; and 2.3) no evidence of hyperkalemia; and 2.4) ACEI / ARB not current at index	2.1) eGFR 30-<60 cc/min/1.72m ² ; and 2.2a) ICD-10 codes I10, I11.x, I12.x, I13.xx, I15.x, I16.x at 1 inpatient or 2 outpatient encounters, or on the problem list, in the previous 2 years, or 2.2b) UMACR >= 30 mg albumin / g creatinine ; and 2.3) no ICD-10 code E87.5 or serum potassium >= 6.5 mg / dl in the previous 2 years; and 2.4) no ACEI / ARB orders with start date before or on index date, or end date on or after index date
BP care gap	3.1) 2 consecutive elevated BP	3.1) index BP and next most recent BP >= 130/80 mm Hg
Glucose care gap	4.1) diagnosed diabetes; and 4.2) A1c above goal	4.1) ICD-10 codes E10, E11 at 1 inpatient or 2 outpatient encounters, or on the problem list, in the previous 2 years; and 4.2) most recent A1c>=7 on or before index date
Nephrology care gap	5.1) Stage 3b or 4 CKD; and	5.1a) most recent eGFR15-<30 cc/min/1.72m ² , or

	5.2) nephrology referral needed	5.1b) eGFR30-<45 cc/min/1.72m ² and UMACR >=30 mg/g; and 5.2) no completed nephrology visit in prior year
--	---------------------------------	---

The index visit is defined as the first visit at any randomized clinic during the accrual period at which the patient met these CKD-CDS intervention eligibility criteria and none of the exclusion criteria. The patient accrual period (for index visits) was 11 months, followed by a 18-month observation period, so that patients will have 18 to 29 months of post-index follow up (estimated median, 24 months).

Each patient was assigned to the clinic where their index visit took place and by extension to the randomized treatment group of that clinic. Patients with index visits at clinics randomized to the CKD-CDS intervention (or usual care) group were considered CKD-CDS intervention (or usual care) patients. A patient could have post-index visits, that may or may not be intervention eligible, at clinics randomized to the other treatment group. Following intent to treat principles, the patient's treatment group assignment will not change as a result of the clinic treatment group assignment or patient intervention eligibility at the post-index visits. Additionally, the index visit marks the beginning of each patient's 18-month observation period.

Web-based eligibility algorithms assess eligibility at all visits in all randomized clinics for the duration of the intervention period. As a result, all patients who have visits during the intervention period will be universally and consistently screened for intervention eligibility without any action, or even awareness, from clinic staff. There is no consenting process for accruing patients into the study, except that patients who have requested to be excluded from all research will be excluded from the study analyses. In sum, neither the patients, clinicians nor study team can influence when a visit is identified as an index visit; and patients who exclude themselves from research are excluded from outcomes analyses. These factors combined minimize the risk of selection into the study denominator to the extent that virtually all intervention eligible patients are included.

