Causes of CKD Care Gaps. Across multiple clinical domains, it is clear that failure of providers to intensify treatment in a timely and appropriate way remains a major obstacle to care improvement.¹⁴⁻²¹ Other obstacles to better CKD care include failure to evaluate a patient for CKD, failure to recognize CKD even when laboratory data substantiate the diagnosis, medication nonadherence, and lack of timely and appropriate referral to nephrology in certain clinical circumstances.²²

Magnitude of CKD Care Gaps (Preliminary Data). Even in relatively high-performing primary care settings, there are remarkably large opportunities for improvement in CKD care. Table 1 shows data on basic elements of CKD care delivered to adults with CKD at HealthPartners Medical Group (HPMG) in Minnesota, where this study will be conducted. HPMG is a multispecialty medical group that partners with Park Nicollet (PN) in a care delivery organization that has been repeatedly recognized nationally for high-quality hypertension control, diabetes care, and excellent overall quality of care. However, recent data provide irrefutable proof that high percentages of adults with CKD fail to meet evidence-based BP, glucose, or ACEI/ARB treatment targets. This is related in part to low rates of CKD recognition and low rates of timely and appropriate referral to nephrology. These pilot data establish that sizeable gaps in quality of CKD care persist even in a well-organized care setting, and attention needs to be directed to specifically improving CKD care.

Table 1: Adults with chronic kidney disease (CKD) by glomerular filtration rate (GFR) stage with quality-of-care data at 17 HealthPartners Medical Group primary care clinics, 2015-2016.

		All eGFR 15-59	3a eGFR 45-59	3b eGFR 30-44	4 eGFR 15-29
A. 1+ eGFR 15-59 cc/min/1.73m ² (N)	N	5766	3823	1559	384
CKD diagnosed	% of A	49.2	36.0	72.2	87.2
diagnosed hypertension	% of A	88.2	85.0	94.0	96.9
BP <140/90 mm Hg	% of A	67.1	69.2	63.5	60.8
BP <130/80 mm Hg	% of A	37.3	38.1	35.8	36.3
B. recognized hypertension or ACR ≥ 30 mg/g	N of A	5107	3263	1470	374
ACEI/ARB current	% of B	57.8	59.4	56.9	48.1
C. diagnosed diabetes or glycated hemoglobin (A1c) >=7%	N of A	2066	1232	638	196
last A1c <8%	% of C	76.7	78.9	72.7	76.0
last A1c <7%	% of C	50.3	51.9	46.2	54.1
D. ACR test rates in patients with GFR evidence of CKD	N of A % of A	1602 27.8	981 25.7	502 32.2	119 31.0

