6.3 MEASURES TO MINIMIZE BIAS

The information exchange between the web service and electronic health record occurs automatically at each visit at the randomized clinics. Algorithms use the information extracted from the electronic health record to systematically assess care gaps, treatment opportunities and safety issues, and then assemble tailored intervention content that incorporates algorithm outputs. As a result, the intervention content made available to front end users is up to date, informed by all available and relevant data and consistent with treatment guidelines across all patients and encounters.

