9.2 SAMPLE SIZE DETERMINATION

We conducted an a priori power analysis for each of the 5 outcome measures to estimate the minimum detectable difference in each given assumptions about analytic sample size, proportions of patients meeting outcome criteria, and intra-class correlations, all estimated from 2015-2016 HPMG pilot data of patients meeting categories for stage 3-4 CKD. The correlated sample of CKD patients within clinics was reduced to an equivalently sized independent patient sample by dividing the anticipated sample size by the design effect introduced by clustering within clinics [Neff pt = N / [1 + (nclus-1)ICCclin]]. For the BP control outcome, the correlated BP sample size (M=Neff pt * m outcomes per patient) was adjusted to account for clustering within patients [Neff obs = M / [1+ (mclus-1)ICCpt]]. Based on the effective sample sizes, we estimated the minimum proportion of CKD-CDS relative to UC patients meeting criteria for each outcome at 12 m that would be powered to reach statistical significance (power=.80, α 2=.05).

Table 2 summarizes for each outcome the sample size, mean and intra-class correlation calculated from HPMG pilot data; the data-informed assumptions used in the power analyses; and the minimum

detectable and clinically meaningful differences among CKD-CDS versus UC patients. Power analysis assumptions were either consistent with or more conservative than pilot estimates. For each outcome, the minimum statistically detectable difference is smaller than the clinically meaningful difference, even under these relatively conservative assumptions. For example, the H1 analysis is powered to detect increases in diagnosis rates of 5.8%-11.1% among CKD-CDS relative to UC patients, a difference that is notably smaller than the 20% increase that would represent significant clinical improvement and should be attainable with the CKD-CDS intervention.

Table 2. Summary of descriptive statistics calculated from HPMG pilot data, key power analysis assumptions, and minimum detectable difference in 12-month post-index outcomes among CKD-CDS relative to UC patients for Hypothesis 1 to 5 outcomes.							
	CKD Dx	ACEI / ARB	BP < 140/90	BP < 130/80	A1c <8	A1c <7	Neph referral
HPMG pilot data estimates							
N ^a	10175	9012	8975	8975	3191	3191	1161
M (%)	52.9	54.6	70.4	43.3	79.7	48.7	37.8
ICC _{clin}	.027	.003	.004	.004	0	.003	0.063
ICC _{pt}			.28	.26			
Power assumptions							
M (%)	50-60	50-60	70-80	40-50	75-85	40-50	30-40

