9.3 POPULATIONS FOR ANALYSES

Individuals who meet all study wide inclusion and exclusion criteria at an index visit as described in Section 5 will be considered for inclusion in the primary analyses. Study-eligible patients will be included in the Hypothesis 1 through 5 according to the care gaps, defined in Section 5.1, that are present at the time of their index visit.

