iv. Interview process: An experienced interviewer and a user interface/ user experience engineer will facilitate the video interview using a GoPro camera and a semi-structured interview guide (attached). The interview guide will be pilot tested with 2 physicians and a project manager to ensure that the questions are clear and well understood. Each interview session will last approximately 30-45 minutes. We will first begin with a general discussion about the participants' baseline understanding of CDS tools and their perception on barriers and facilitators to using CDS tools in the context of their own practice. We believe that it would be helpful to get unbiased feedback about physician attitude towards use of CDS tools prior to introducing them to the CKD-CDS tool. After that, we will ask participants questions relating to the CKD-CDS tool. The programmer will take the provider through the tool using a test patient. The interviews will be audio or video recorded with the consent of the participants and transcribed verbatim. Analysis will involve a continuous iterative process whereby data from the interviews will be re-examined and identified concepts will be explored in subsequent interviews. The analysis will be cumulative and iterative building on the discussions from previous interviews (for example, interview questions and the CKD prototype design will be modified and refined for subsequent interviews) until themes reach saturation.

Preliminary data analysis and chart reviews

During the pilot test and throughout the patient accrual period of the intervention, we will perform preliminary data pulls and chart reviews of no more than 1% of the patients to assess the functioning of the CKD-CDS tool and the effect of the tool on patient care. We will also do chart audits in response to patient and provider feedback sent via the feedback tab found in the online version of the CKD-CDS tool to assess the problems and provide accurate feedback.

Data Collection Following the Launch of the Intervention

i. Process steps for identification of patients and patient records

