10.3 ABBREVIATIONS

A1c	glycated hemoglobin A1
ACC/AHA	American College of Cardiology/American Heart Association
ACE	affiliated covered entities
ACEI	angiotensin converting enzyme inhibitor
ACR	albumin to creatinine ratio
AE(s)	Adverse Event(s)
ARB	angiotensin receptor blocker
ASCVD	Atherososclerotic cardiovascular Disease
BP	Blood pressure
BPA	Best Practice Advisory
CDS	Clinical Decision Support
CFR	Code of Federal Regulations
CKD	chronic kidney disease
CRF	Case Report Form
CV	Cardiovascular
DSMB	Data Safety Monitoring Board
ED	Emergency Department
eGFR	estimated glomerular filtration rate
EHR	Electronic Health Record
EMR	Electronic Medical Record
FDA	Food and Drug Administration
GCP	Good Clinical Practice
HIPAA	Health Insurance Portability and Accountability Act
HP	HealthPartners
HPMG	HealthPartners Medical Group
HTTPS	Hypertext Transfer Protocol Secure
ICD-10	10th revision of the International Statistical Classification of Diseases and Related Health Problems
ICH	International Conference on Harmonisation
ID	Identification
IRB	Institutional Review Board
MAR	missing at random
MDH	Minnesota department of health
mg/dl	milligrams/deciliter
mm Hg	Millimeters of Mercury
NCT	National Clinical Trial
NIH	National Institutes of Health
NSAID(s)	non-steroidal anti-inflammatory drug(s)
OHRP	Office for Human Research Protections
PCP(s)	Primary Care Provider(s)
PEM	Patient education material(s)

PHI	personally identifiable health information
PI	Principal Investigator
PN	Park Nicollet
SAE(s)	serious adverse event(s)
SDM	Shared decision making
SOAP	Simple Object Access Protocol
SSL	Secure Sockets Layer
UC	usual care
UMACR	urine micro-albumin creatinine ratio
UP(s)	unanticipated problem(s)

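### The potassium cut-off in the ACEI/ARB care gap is printed in mg/dl, which contradicts the rule's own label and, if applied literally, would severely deplete the H2 analysis set

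*Combined protocol and SAP*

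**What the plan says.** The section 5.1 care-gap table describes each condition in words and then gives its operational rule. For the ACEI/ARB gap, condition 2.3 reads in words "2.3) no evidence of hyperkalemia; and" and operationally "no ICD-10 code E87.5 or serum potassium >= 6.5 mg / dl in the previous 2 years". The abbreviation list in section 10.3 expands mg/dl as "milligrams/deciliter", so the printed unit is a defined mass concentration.

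The rule feeds the primary analysis directly. Section 9.3 states: "Study-eligible patients will be included in the Hypothesis 1 through 5 according to the care gaps, defined in Section 5.1". Item 2.3 therefore helps to decide who is analysed for H2 (ACEI/ARB use).

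It is applied by program. Section 6.3 says: "Algorithms use the information extracted from the electronic health record to systematically assess care gaps, treatment opportunities and safety issues". Section 5.1 adds that clinic staff play no part in the screening.

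No other section gives a potassium cut-off or unit. Section 7.1 mentions abnormal potassium only in general terms, and Hypothesis 2 in section 9.1 does not mention potassium.

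**The concern.** The number, the unit and the label in item 2.3 cannot all hold. A cut-off of 6.5 in the printed unit lies far below any plausible serum value, so the rule as written treats ordinary results as hyperkalaemia. The label says the opposite is intended.

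This is an operational threshold in the definition of a primary analysis set, so it matters more than a unit slip in background text. It is run by algorithm, with no clinician in the loop to notice an implausible flag. Section 10.1.9.1 also plans to bring data from several sources into one format, which is the step at which a stated unit gets used. Anyone who coded the H2 cohort or tried to replicate it from the printed rule, converting the laboratory feed to mg/dl, would lose most or nearly all tested patients. Because section 5.1 requires at least one gap for an index visit, patients whose only gap was this one would then drop out of the study altogether.

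**Working it through.** **Inputs.**
- Cut-off 6.5, unit mg/dl, look-back 2 years: section 5.1, item 2.3.
- H2 planning figures: Table 1 row B, "B. recognized hypertension or ACR ≥ 30 mg/g", 5,107 patients in 17 clinics; Table 2, N = 9,012 prorated to 30 clinics, pilot rate 54.6%, assumed rate 50-60%, clinic ICC .001-.01, detectable difference 3.4-5.7 points, meaningful difference 10 points; error rates "power=.80, α 2=.05".
- Not in the documents: the molar mass of potassium, 39.098 g/mol (a physical constant); an assumed range of measured outpatient potassium of 3.0-6.0 mmol/L; and the share of H2 candidates with a potassium result in 2 years, varied below from 50% to 100%.

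**1. The plan's own H2 figures.** 5,107 × 30/17 = 9,012.4, against 9,012 stated. With 9,012/30 = 300.4 patients per clinic, the effective sample size is N / [1 + (300.4 − 1) × ICC]:
- ICC .001: 9,012 / 1.2994 = 6,936
- ICC .01: 9,012 / 3.994 = 2,256

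Solving for the difference detectable with 80% power, two-sided 0.05 and equal arms gives 3.4 points (rate 50%, ICC .001) and 5.7 points (rate 60%, ICC .01), as stated. At 50% and ICC .01 it is 5.9. Row B carries no potassium condition, so item 2.3 does not enter these figures.

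**2. Unit conversion.** mmol/L = (mg/dl × 10) / 39.098.
- 6.5 mg/dl = 65 / 39.098 = 1.66 mmol/L
- 3.0 mmol/L = 11.7 mg/dl and 6.0 mmol/L = 23.5 mg/dl
- 6.5 on the mmol/L scale would be 25.4 mg/dl, so the two readings differ by a factor of 3.91

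The whole assumed range lies above 6.5 mg/dl. The conclusion does not depend on the exact range, only on measured values exceeding 1.66 mmol/L.

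**3. Effect on H2 if the printed unit were applied.** Candidates with any potassium result in 2 years fail item 2.3. Those with no result and no E87.5 code stay in. Table 2's N includes patients already on an ACEI/ARB, so a rough proxy for the candidates is 9,012 × (1 − 0.546) = 4,091. This proxy ignores the stage 3, age and two-eGFR criteria. The number remaining is 4,091 × (1 − share tested). The last column uses the method of step 1 with 30 clinics, an illustrative 50% rate and ICC .001 to .01.

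| Share with a potassium result | Patients remaining | Detectable difference (points) |
|---|---|---|
| none removed | 4,091 | 4.7-6.7 |
| 50% | 2,046 | 6.4-8.0 |
| 80% | 818 | 9.9-10.9 |
| 90% | 409 | 13.8-14.5 |
| 95% | 205 | 19.2-19.6 |
| 99% | 41 | not computed |
| 100% | 0 | none |

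At 80% tested, the detectable difference reaches about the 10 points that Table 2 calls meaningful. The set is empty only at 100%.

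**The case against.** The strongest defence is that this is a clerical slip that never reached the code. The row states its intent in words. Unit labels in this table are loosely typed: it prints body-surface area as 1.72 m², while criterion 2 just above it, and sections 9.1 and 9.4.2.2, print 1.73. If the algorithm compares 6.5 with a stored value in mmol/L or mEq/L, the printed label changes nobody's status. There were also chances to notice a nearly vacant gap: "preliminary data pulls and chart reviews of no more than 1% of the patients to assess the functioning of the CKD-CDS tool" in section 10.1.9.1, range checks on each variable in the same section, correction of coding bugs described in section 6.4, and anomaly reporting in section 10.1.8.

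Most of this stands. A slip is the likeliest explanation, and nothing shows that mg/dl was coded. But no section states the coded unit, the unit of the feed, the size of the H2 set, or what the checks found for this item. The defence makes harm unlikely; it does not make the printed rule correct.

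A reader might infer four stronger conclusions, none of which the documents support:
- *The H2 set is emptied.* Untested patients without an E87.5 code remain. Eligibility requires two eGFR results, so a high share with potassium results is plausible, but that is an assumption.
- *The safety screen is reversed.* The literal rule over-excludes. Patients with truly high results still fail it, the diagnosis-code limb has no unit, and untested patients pass under either unit. No additional patient is let through.
- *The arms are selected differently.* Section 6.1.1 says the tool runs silently in usual-care clinics so that eligible patients are identified in the same way. The question is who is analysed for H2, not imbalance by arm.
- *The power calculation is wrong.* Step 1 of the working shows that Table 2 never used the potassium rule.

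**Conclusion.** The point holds as an error in an operational eligibility rule. Item 2.3 as printed sets the cut-off at about 1.66 mmol/L, contradicts its own label, and is corrected nowhere else. That conclusion rests only on the printed text and the molar mass of potassium.

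The consequence for H2 is conditional. If the printed unit was applied, the set would be severely depleted and would consist mainly of patients without a recent potassium test. The counts above are illustrative, because the share tested is unknown and 4,091 is a rough proxy. If the algorithm and the cohort program compared 6.5 with values in mmol/L or mEq/L, the H2 set is unaffected. The documents do not settle which applies. The correction should be made because the rule defines a primary analysis set and the check is cheap. No view is taken on which potassium threshold is clinically right.

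**What to change.** 1. Reconcile the number, unit and label in item 2.3, stating the unit in which the laboratory feed delivers potassium. The threshold itself is for the sponsor to decide.
2. Confirm in writing that the decision-support algorithm and the H2 cohort program use the same cut-off and unit as the corrected text.
3. Re-derive the H2 set only if either program applied mg/dl.
4. In the same edit, word item 2.3 so that it plainly requires neither the diagnosis code nor a high result. The present no-A-or-B phrasing can be misread, although the label supports the neither-nor reading.

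The cost is one table entry and one check of the eligibility code. Table 2 needs no change on this account.
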